### **10.2 Analysis of Secondary Endpoints**

Secondary Efficacy Endpoints are:

- All-cause mortality: calculated as number of deaths of any cause from randomization to Day 28 divided by the number of subjects in the treatment group. All deaths will be entered as SAEs in the AE CRF. Thus, the information will be obtained from the AE CRF as SAEs with outcome “Death Related to Adverse Event” and SAE end date (death date) occurring within the 28 days of the Treatment Period.
- Incidence of tracheal intubation from randomization to Day 28: calculated as number of subjects experiencing intubation from randomization to Day 28 divided by the number subjects in the treatment group. Tracheal intubation is defined as presence of a record for this procedure (“Endotracheal Intubation” ticked on the Respiratory Support CRF) with a start date during the 28 days of the Treatment Period.
- Proportions of subjects using CPAP or BiPAP: calculated as number of subjects using CPAP or BiPAP within 28 days of randomization divided by the number subjects in the treatment group. Use of CPAP or BiPAP is defined as presence of a record for this procedure (“CPAP” or “BiPAP” ticked on the Respiratory Support CRF) with a start date during the 28 days of the Treatment Period.
- Proportion of subjects using HFNC: calculated as number of subjects using HFNC within 28 days of randomization divided by the number subjects in the treatment group. Use of HFNC is defined as presence of a record for this procedure (“HFNC” ticked on the Respiratory Support CRF) with a start date during the 28 days of the Treatment Period.

- Proportion of subjects using ECMO: calculated as number of subjects using ECMO within 28 days of randomization divided by the number subjects in the treatment group. Use of ECMO is defined as presence of a record for this procedure (“ECMO” ticked on the Respiratory Support CRF) with a start date during the 28 days of the Treatment Period.
- Clinical status assessed on an 8-point NIAID ordinal scale as entered in the CRF.
- Length of hospital stay defined as time interval from randomization to hospital discharge alive. The information will be derived from the SARS-CoV-2 CRF along with the AE CRF for the survival status (no SAE with outcome “Death Related to Adverse Event” reported).
- Subject’s maximum SOFA score, subject’s maximum change from baseline in SOFA score, and subject’s mean SOFA score during the study will be calculated.

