 - Respiratory frequency $>$ 30 breaths per minute
 - Saturation of peripheral (capillary) oxygen (SpO_2) \leq 93% on room air
 - Ratio of partial pressure of arterial oxygen to fraction of inspired oxygen (PaO_2/FiO_2) $<$ 300
 - Arterial oxygen saturation (SaO_2)/ FiO_2 ratio $<$ 218 (if PaO_2/FiO_2 ratio is not available)
 - Radiographic lung infiltrates $>$ 50%

Exclusion criteria:

1. Currently enrolled, planning to enroll, or participated, within the last 30 days, in a clinical study requiring administration of an IP, including expanded access or compassionate use with the only exception being administration of convalescent plasma. Administration of IP is permitted only if an emergency use authorization has been granted (eg, remdesivir). Additionally, off-label use of approved drugs (eg, anti-IL-6/anti-IL-6R) is also permitted.
2. Pregnant or breastfeeding (female subjects)
3. Intubated or requires mechanical ventilation (including ECMO) at the time of randomization
4. In the opinion of the investigator, the subject is expected to be intubated within the first 24 hours after IP administration

5. Active Do-Not-Intubate (DNI) or Do-Not-Resuscitate (DNR) order
6. In the opinion of the investigator, the subject is not expected to survive for > 48 hours
7. Any of the following comorbid conditions prior to randomization and prior to SARS-CoV-2 infection:
 - Severe heart failure (New York Heart Association Class IV)
 - End-stage renal disease (Stage \geq 4) or need for renal replacement therapy
 - Biopsy-confirmed cirrhosis, portal hypertension, or hepatic encephalopathy
 - Malignancy (Stage IV)
 - Chronic lung disease requiring the use of oxygen at home
 - Active tuberculosis disease
8. Active bleeding or current clinically significant coagulopathy (eg, international normalized ratio [INR] > 1.5) or clinically significant risk for bleeding (eg, recent intracranial hemorrhage or bleeding peptic ulcer within the last 4 weeks)
9. History of venous thrombosis, myocardial infarction, or cerebrovascular event within the last 3 months, or a prothrombotic disorder (eg, antithrombin III, protein C, or protein S deficiency)
10. Known or suspected Grade 3 or 4 infusion-related reaction or hypersensitivity (per Common Terminology Criteria for Adverse Events) to monoclonal antibody therapy, or hypersensitivity to the IP or any excipients of the IP [National Cancer Institute, 2009]
11. Currently receiving a therapy not permitted during the study

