Sensitivity analyses to assess the effect of missing data will be conducted, for example, by performing tipping point analyses that vary assumptions about the missing outcomes in both study treatment groups.

Other Analyses

Details of the analyses of secondary efficacy, safety, PK, CCI are provided in the full clinical study protocol.

- i. A physical examination will be conducted per the study site's standard procedure.
- j. The subject's height and body weight will only be measured at Screening.
- k. Vital sign assessments, including blood pressure (systolic and diastolic), heart rate, and body temperature, should be assessed and recorded in the eCRF at approximately the same time each day during study participation. Blood pressure and heart rate will be measured with the subject in a supine or seated position after resting for ≥ 5 minutes. Body temperature will be measured either sublingually or tympanically; body temperature may also be measured using a non-contact infrared thermometer. The method of measurement should be consistent throughout the study for a given subject.
- l. Respiratory parameters: respiratory rate (breaths per minute), SpO₂ (%), and FiO₂ (natural air includes 21% oxygen, which is equivalent to FiO₂ of 0.21). Respiratory parameters should be measured once daily, ideally performed together with vital signs at the same time of the day.
- m. PaO₂ should be measured only on days when the SOFA score is assessed. An indwelling arterial catheter should not be placed just to collect these samples. Although the PaO₂/FiO₂ ratio is preferable to calculate the SOFA score, if PaO₂ is not available, the SaO₂/FiO₂ ratio may be used instead.
- n. These assessments will be performed at the local laboratory.
- o. A urine test for β -hCG will be performed at the local laboratory for all female subjects of childbearing potential to rule out pregnancy during Screening and at the end of the Treatment Period. A serum pregnancy test will be performed by the site if urine result is inconclusive.
- p. Blood samples will be analyzed for the laboratory parameters specified in Table 3.
- q. IP will be either IV CSL312 +SOC or IV placebo +SOC.
- r. Blood samples will be analyzed at the central laboratory for the PK parameters specified in Section 7.4 CCI. Analysis of the PK data will be performed by CSL (or delegate).
- s. On Day 1, blood samples will be collected at 30 minutes and 6 hours after the end of the infusion of IP to perform PK assessments.

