2.2.2 Secondary Endpoints

Secondary Objectives	Endpoints	Summary Measures
1	All-cause mortality	Proportion of deaths from all causes occurring from randomization to Day 28
1	Incidence of tracheal intubation	Proportion of subjects intubated from randomization to Day 28

Secondary Objectives	Endpoints	Summary Measures
1	Clinical status as assessed on an 8-point National Institute of Allergy and Infectious Diseases (NIAID) ordinal scale (Appendix 3)	
 • Number and proportion of subjects with ≥ 2-point improvement in the ordinal scale • Number and proportion of subjects within each of the categories of the ordinal scale
1	Use of continuous positive airway pressure (CPAP) or bi-level positive airway pressure (BiPAP)	Proportion of subjects using CPAP or BiPAP
1	Use of high-flow nasal cannula (HFNC)	Proportion of subjects using HFNC
1	Use of extracorporeal membrane oxygenation (ECMO)	Proportion of subjects requiring ECMO
1	Change in Sequential Organ Failure Assessment (SOFA) score (Appendix 2)	
 • Median of maximum change from Baseline in SOFA score • Change from Baseline in SOFA score and in the individual components of SOFA score
1	Hospital length of stay (LOS)	
 • Median LOS in hospital stay

Secondary Objectives	Endpoints	Summary Measures
2	Subjects experiencing the following safety events: 
 • Adverse events (AEs) • Serious adverse events (SAEs) • Adverse events of special interest (AESIs) • CSL312-induced anti-CSL312 antibodies • Clinically significant abnormalities in laboratory assessment that are reported as AEs 	Number and proportion of subjects experiencing the specified safety events after treatment with CSL312 or placebo
3	CSL312 PK in plasma: 
 • Maximum plasma concentration (C_{max}) • Time to maximum plasma concentration (T_{max}) • Area under the plasma concentration-time curve from time zero to the time of the last measurable concentration (AUC_{0-last}) • Terminal half-life ($T_{1/2}$) 	
 • Mean (\pm SD) and geometric mean (geometric coefficient of variation percentage [CV%]) for all PK parameters except T_{max}. • Median (minimum, maximum) for T_{max}

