6.2 Inclusion Criteria

To be enrolled and randomized into the study, subjects must meet all of the following inclusion criteria:

1. Capable of providing written informed consent. An individual legally permitted to make medical decisions on the subject's behalf can provide written informed consent
2. Willing and able to adhere to all protocol requirements
3. Age \geq 18 years at the time that informed consent is obtained

4. Positive for SARS-CoV-2 infection as determined using a molecular diagnostic test (reverse transcription polymerase chain reaction [RT-PCR] or equivalent) approved by regulatory authorities (including Food and Drug Administration [FDA] or Brazilian Health Regulatory Agency [ANVISA]) or allowed under an emergency use authorization within 14 days before Screening. If a false negative result is suspected, the SARS-CoV-2 test may be repeated within the Screening Period.
5. Chest computed tomography (CT) scan or X-ray results confirming interstitial pneumonia
6. Severe COVID-19 disease as evidence by ≥ 1 of the following criteria at Screening including within 24 hours before Screening:
 - Respiratory frequency > 30 breaths per minute
 - Saturation of peripheral (capillary) oxygen (SpO_2) $\leq 93\%$ on room air
 - Ratio of partial pressure of arterial oxygen to fraction of inspired oxygen (PaO_2/FiO_2 ratio) < 300
 - Ratio of arterial oxygen saturation to fraction of inspired oxygen (SaO_2/FiO_2 ratio) < 218 (if PaO_2/FiO_2 ratio is not available)
 - Radiographic lung infiltrates $> 50\%$

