6.3 Exclusion Criteria

Subjects must not be enrolled into the study or randomly assigned to treatment if they meet any of the following exclusion criteria:

1. Currently enrolled, planning to enroll, or participated, within the last 30 days, in a clinical study requiring administration of an IP, including expanded access or compassionate use with the only exception being the administration of convalescent plasma. Administration of IP is permitted only if an emergency use authorization has been granted (eg, remdesivir). Additionally, off-label use of approved drugs (eg, anti-IL-6/anti-IL-6R) is also permitted.
2. Pregnant or breastfeeding (female subjects)
3. Intubated and require mechanical ventilation (including ECMO) at the time of randomization

4. In the opinion of the investigator, the subject is expected to be intubated in the first 24 hours after IP administration
5. Active Do-Not-Intubate (DNI) or Do-Not-Resuscitate (DNR) order
6. In the opinion of the investigator, not expected to survive for > 48 hours after admission
7. Presence of any of the following comorbid conditions prior to randomization and prior to SARS-CoV-2 infection:
 - Severe heart failure (New York Heart Association Class IV)
 - End-stage renal disease (Stage \geq 4) or need for renal replacement therapy
 - Biopsy-confirmed cirrhosis, portal hypertension, or hepatic encephalopathy
 - Malignancy (Stage IV)
 - Chronic lung disease requiring the use of oxygen at home
 - Active tuberculosis disease
8. Active bleeding or a current clinically significant coagulopathy (eg, international normalized ratio [INR] > 1.5) or clinically significant risk for bleeding (eg, recent intracranial hemorrhage or bleeding peptic ulcer within the last 4 weeks)
9. History of venous thrombosis, myocardial infarction, or cerebrovascular event within 3 months, or a prothrombotic disorder (eg, antithrombin III, protein C, or protein S deficiency)
10. Known or suspected Grade 3 or 4 infusion-related reaction or hypersensitivity (per Common Terminology Criteria for Adverse Events [CTCAE]) to monoclonal antibody therapy, or hypersensitivity to the IP or any excipients of the IP [[National Cancer Institute, 2009](#)]
11. Currently receiving a therapy not permitted during the study (see [Section 9.1](#))

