### **8.3 Study Periods Relative to Treatment**

**Screening Period** starts with the date (and time) of the signed informed consent and ends before the date (and time) of randomization.

**Treatment Period** starts with the date (and time) of randomization and ends on the Day 28 visit.

**EOS** is at Day 28, the last day of the Treatment Period.

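### SAP 10.2 labels two secondary endpoints as use of HFNC and of CPAP/BiPAP but counts only starts after randomisation, so use is under-reported if ongoing support is not re-recorded

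*SAP*

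**What the plan says.** Protocol 2.2.2 gives the HFNC summary measure as "Proportion of subjects using HFNC" and words the CPAP/BiPAP measure in the same way. Neither is limited to new starts.

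SAP 10.2 describes the HFNC proportion as "calculated as number of subjects using HFNC within 28 days of randomization divided by the number subjects in the treatment group", with a parallel sentence for CPAP/BiPAP. It then defines use as a record with the device "ticked on the Respiratory Support CRF) with a start date during the 28 days of the Treatment Period". Under SAP 8.3 the Treatment Period "starts with the date (and time) of randomization and ends on the Day 28 visit".

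SAP 10.2.1 reports risk differences, confidence intervals and one-sided p-values for these endpoints from the primary model. Subjects who leave early without a qualifying record count as non-events. SAP section 5 declares no departure from the protocol's planned analyses.

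On entry, exclusion 3 in the protocol synopsis reads "Intubated or requires mechanical ventilation (including ECMO) at the time of randomization", while Protocol 6.3 reads "Intubated and require mechanical ventilation (including ECMO) at the time of randomization". Neither version names HFNC, CPAP or BiPAP.

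**The concern.** Someone on HFNC at randomisation who stays on it afterwards is using HFNC during the 28 days. If the only record began before randomisation, the SAP rule scores that subject as a non-user and keeps the subject in the denominator. No SAP section counts support already running, and none says that it is re-entered with a new start date.

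At stake is the level that will be published under the label of use, and the meaning of the p-value beside it, which comes from a model of initiation. The planned outputs would not reveal the gap. The SAP 9.3 baseline summaries list no respiratory support, and category 3 of the NIAID scale (SAP 15.3) pools NIV with high-flow oxygen, so use of each device cannot be recovered from them.

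**Working it through.** **Can subjects be on these devices at randomisation?** HFNC is not excluded. CPAP/BiPAP probably is not: Protocol 1.1 treats NIV as a step before mechanical ventilation, and the NIAID scale puts NIV in category 3, apart from invasive ventilation in category 2. The synopsis and body versions of exclusion 3 differ (*or* against *and*) and must be reconciled.

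Entry on substantial oxygen is foreseen. One qualifying criterion in Protocol 6.2 is a value below 218 for the "Ratio of arterial oxygen saturation to fraction of inspired oxygen", used if PaO2/FiO2 is not available. The Schedule of Assessments, footnote l, states that "natural air includes 21% oxygen".
- On room air: 218 × 0.21 = 45.8, so SaO2 would have to be below 46%.
- At an assumed SaO2 of 90%: 90 / 218 = 0.413, so FiO2 must exceed 0.41.

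This shows supplemental oxygen at entry, but not the device that delivers it.

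**Inputs.** The documents state no figure for HFNC or CPAP/BiPAP use, so there is none to reproduce. The denominator is the planned 62 per arm (Protocol 11.1). That number does reproduce from 30% against 10%, two-sided alpha 0.05, with 80.3% power. Three quantities are assumed:
- b, the share on the device at randomisation;
- q, new use among the rest;
- c, the share of baseline users whose support stays on a record begun before randomisation.

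**Formulas**
- Use = b + (1 − b)q
- Initiation among all randomised = (1 − b)q
- SAP figure = (1 − b)q + b(1 − c)
- Shortfall = use − SAP figure = b × c

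**Level, with q = 30%**

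| b | Use | SAP figure, c = 100% | Shortfall | SAP figure, c = 50% | Shortfall | Baseline users per arm (62b) |
|---|---|---|---|---|---|---|
| 10% | 37% | 27% | 10 points | 32% | 5 points | 6.2 |
| 30% | 51% | 21% | 30 points | 36% | 15 points | 18.6 |
| 50% | 65% | 15% | 50 points | 40% | 25 points | 31 |

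With c = 0 the shortfall is zero.

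**Comparison of arms, with q = 30% against 15%, c = 100% and equal b.** The risk difference is (1 − b) × 15 points for both initiation and use: 13.5, 10.5 and 7.5 points at b = 10%, 30% and 50%. Among subjects not on the device it is the full 15 points.

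Expected z (unpooled, unadjusted) at b = 30%:
- SAP rule, n = 62 per arm: 0.105 / √[(0.21 × 0.79 + 0.105 × 0.895)/62] = 1.62
- Total use, n = 62 per arm: 0.105 / √[(0.51 × 0.49 + 0.405 × 0.595)/62] = 1.18
- Initiation among those not on the device, n = 62 × 0.7 = 43.4 per arm: 0.15 / √[(0.30 × 0.70 + 0.15 × 0.85)/43.4] = 1.70

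**Unequal b, no treatment effect (q = 30% in both arms, c = 100%).** With b = 35% on CSL312 and 25% on placebo, initiation is 19.5% against 22.5% (−3 points) and use is 54.5% against 47.5% (+7 points).

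**The case against.** The strongest reply is that *use* is a defined term in SAP 10.2. The protocol gives no time window or record rule for it, so the SAP had to supply one and does so openly. The rule is also the better one for comparing arms: expected z is 1.62 against 1.18 for total use, and a chance imbalance in baseline support disturbs it less (−3 against +7 points above). Use mixes in a state that precedes randomisation and that treatment cannot change.

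That stands as an argument for analysing initiation. It does not justify calling the result use, when the preceding sentence of the SAP and the protocol endpoint both say something wider.

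It also stands that b and c are unknown. The CRF completion rules are not in the documents, and if every ongoing episode is re-entered after randomisation the shortfall disappears. The SaO2/FiO2 criterion is one of five alternatives and does not identify a device. Exclusion 4 (intubation expected within 24 hours) points away from the heaviest support at entry. NIAID category 3 at baseline would give an upper limit on the share on either device, and the separate table shells may contain more. These points limit what can be said about size; they do not remove the mismatch.

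Finally, these are descriptive secondary endpoints (SAP 10.3). That bears on how much the point matters, not on whether it is right.

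**Conclusion.** The concern holds. As written, SAP 10.2 reports initiation after randomisation among all randomised subjects under the name of use, and SAP section 5 declares no change from the protocol. The level of use is understated by b × c. On assumed inputs that runs from zero to 50 points; at b = 30%, q = 30% and c = 100%, 21% is reported where 51% used the device, with about 19 of 62 subjects per arm scored as non-users.

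The error lies in the label and the level. With balanced baseline use and no re-entry the risk difference equals that for use, though it is smaller by the factor (1 − b) than the difference among subjects not yet on the device. No systematic bias towards one arm is shown, and the primary endpoint is untouched. The CPAP/BiPAP part rests on reading exclusion 3 as not covering NIV; the HFNC part does not. It should be corrected because the remedy is cheap, but it does not threaten the trial's main conclusion.

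**What to change.** In SAP 10.2, for HFNC and CPAP/BiPAP only:

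1. Report use by also counting records that began before randomisation and are ongoing at randomisation. Keep this descriptive, given the lower expected z.
2. Rename the start-date version *initiation after randomisation* and compare arms among subjects not on that device at randomisation.
3. Take device status from the last value before randomisation, as in SAP 8.2.3, keeping that section's pre-dose fallback only where no earlier value exists. Using the pre-dose Day 1 value routinely could reclassify support started between randomisation and dosing.
4. Show the number already on each device at randomisation, by arm.
5. State whether starts on the day of randomisation are compared by date or by date and time, and footnote that a switch between devices counts as initiation of the second.

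ECMO and intubation can stay as written, since exclusion 3 addresses both. Its two versions still need to be reconciled.

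**Cost.** SAP wording, one derivation and one baseline row, provided the CRF holds the data. That must be checked: SAP section 3 cites CRF Version 1.0 of 03 Jun 2020, whereas the pre-dose assessment of these devices was added by Amendment 2 of 25 August 2020. If the CRF already re-enters every ongoing episode, use is already counted correctly and a sentence saying so closes the point on level; the initiation comparison would then need its own derivation. It would rest on fewer subjects (about 43 of 62 per arm at b = 30%) with no loss in expected z (1.70 against 1.62).

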### 10.2.1 Secondary Efficacy Analysis

The ITT and mITT Analysis Set will be used for the secondary efficacy analyses. Number and percentage of subjects will be presented by treatment for the following secondary efficacy endpoints:

- All-cause mortality;
- Incidence of tracheal intubation;
- Proportion of subjects using CPAP or BiPAP;
- Proportion of subjects using HFNC;
- Proportion of subjects using ECMO.

The same statistical model and testing methodology as used for the primary efficacy variable will be used to compare the above secondary efficacy endpoints between the 2 treatments. The risk differences, associated 95% CIs, and 1-sided p-values will be reported.

Subjects with less than 28 days of the Treatment Period and without documented secondary endpoints as defined above will be assumed as not having experienced the secondary endpoint.

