11.1 Sample Size

There are limited data on the rates of subjects with COVID-19 who progress to tracheal intubation or death prior to tracheal intubation within 28 days. For sample size calculation, a rate of 30% in the control group and a rate of 10% in the CSL312 group have been assumed. With a 2-sided $\alpha = 0.05$ and 1:1 randomization ratio for CSL312 + SOC versus placebo + SOC, a total of 124 subjects need to be randomized (62 subjects to CSL312 + SOC and 62 subjects to placebo + SOC) in order to achieve 80% power to detect a treatment difference using a 2 group chi-square test. For the sample size calculation, it is further confirmed using simulations performed in East[®] 6.5 software (Cytel, Inc.: Waltham, MA) that 80% power is maintained, accounting for the interim analysis for futility and sample size re-estimation.

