11.4 Analyses of Secondary Efficacy

The following secondary efficacy endpoints will be summarized by treatment group using subject count and percentage:

- All-cause mortality
- Incidence of tracheal intubation from randomization to Day 28

- Proportions of subjects using CPAP or BiPAP
- Proportion of subjects using HFNC
- Proportion of subjects using ECMO

The same testing method used for the primary efficacy variable will also be used to compare the above secondary efficacy endpoints between the 2 treatment groups. The proportion differences, associated 95% CIs, and 2-sided p-values will be reported.

Clinical Status Assessed on an 8-Point NIAID Ordinal Scale

Frequency and proportion of subjects within each category of the 8-point NIAID ordinal scale will be summarized along with graphical displays for each treatment group. Frequency and proportion of subjects with an improvement from Baseline of ≥ 2 points will be analyzed using descriptive statistics.

Hospital Length of Stay

Hospital LOS is defined as the time interval from randomization to hospital discharge alive. In this analysis, for subjects who did not have hospital discharge (ie, no recorded date of hospital discharge) and did not die, the time to hospital discharge will be censored at the last known in-hospital date if the subject did not complete the 28-day Treatment Period. For subjects who do not have a hospital discharge event or censoring time within the 28 days after randomization or for subjects who have died, an administrative censoring will be applied at 28 days.

Hospital LOS will be analyzed using Cox model including treatment group; age as a continuous covariate; gender (male or female), country (USA or Brazil); and comorbidities (yes or no) as categorical covariates in the model. Hazard ratio, its 95% CI and 2-sided Wald p-value for hypothesis-testing will be estimated from the model. Cumulative event rates will be calculated using the Kaplan-Meier (KM) method. The effect over time will be illustrated with a plot of the complement ($1 - KM$) of KM estimates. Event counts and percentages will be summarized. If ties occur, Efron's method will be used to adjust for ties.

Sequential Organ Failure Assessment

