## 4.4 Determination of the Initial Sample Size

There are limited data on the rates of subjects with COVID-19 who progress to tracheal intubation or death prior to tracheal intubation within 28 days. For sample size calculation, a rate of 30% in the control group and a rate of 10% in the CSL312 group have been assumed. With a 1-sided  $\alpha = 0.025$  (which is equivalent to a 2-sided  $\alpha = 0.05$ ) and 1:1 randomization ratio for CSL312 + SOC versus placebo + SOC, a total of 124 subjects need to be randomized (62 subjects to CSL312 + SOC and 62 subjects to placebo + SOC) to achieve 80% power to show superiority using a 2 group chi-square test. For the sample size calculation, it is further confirmed using simulations performed in East 6.5 that 80% power is maintained, accounting for the interim analysis for futility and sample size re-estimation.

Depending on the results after the interim analysis, the sample size may be increased up to 248 subjects (124 subjects in CSL312 + SOC and 124 subjects in placebo + SOC).

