## 5 Changes from the Protocol Planned Analyses

There are no changes to the analyses planned as specified in the study protocol.

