### **Hospital Length of Stay**

Hospital LOS will be defined as the time interval from randomization to hospital discharge alive. Survival status will be obtained from the AE CRF as absence of an SAE with outcome “Death Related to Adverse Event”. In this analysis, for subjects who did not have a recorded date of hospital discharge and did not die, the time to hospital discharge will be censored at the last known in-hospital date if the subject did not complete the 28-day Treatment Period (i.e., the date of premature study discontinuation). For subjects who do not have a hospital discharge event or censoring time within the 28 days after randomization or for subjects who have died, an administrative censoring will be applied at 28 days.

Hospital LOS will be analyzed using Cox proportional hazard model including age as a continuous covariate, treatment group, gender (male or female), country (USA or Brazil), and baseline comorbidities (yes or no) as categorical covariates in the model. The hazard ratio, its 95% CI and 1-sided Wald p-value will be estimated from the model. Cumulative event rates will be calculated using the Kaplan-Meier (KM) method. The effect over time will be illustrated with a plot of the complement (1 – KM) of the KM estimates. Event counts and percentages will be summarized. If ties occur, Efron’s method will be used to adjust for ties.

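### The SAP makes the protocol's 2-sided p-values 1-sided without declaring it; the primary decision is unaffected, but the printed secondary p-values change

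*SAP*

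**What the plan says.** **Protocol.** Section 11.1 sizes the trial "With a 2-sided $\alpha = 0.05$ and 1:1 randomization ratio". Section 11.3 takes a 2-sided p-value from the Firth model for the primary endpoint. Section 11.4 applies the same testing method to all-cause mortality, tracheal intubation, CPAP or BiPAP use, HFNC use and ECMO use: "The proportion differences, associated 95% CIs, and 2-sided p-values will be reported". For hospital length of stay it specifies a 2-sided Wald p-value from the Cox model. For the Wilcoxon test on SOFA scores it gives no sidedness.

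**SAP.** Section 4.1.2 writes the alternative hypothesis as lower risk on CSL312. Section 4.4 restates the design level as 1-sided 0.025, "which is equivalent to a 2-sided" level of 0.05. Section 7 makes 1-sided testing at 0.025 the default for every test. Section 10.1.2 rejects the primary null hypothesis at 1-sided p below 0.025. Section 10.2.1 carries the primary model and testing method to the same five binary secondaries: "The risk differences, associated 95% CIs, and 1-sided p-values will be reported". For length of stay: "The hazard ratio, its 95% CI and 1-sided Wald p-value will be estimated from the model". Section 10.3 names one confirmatory test and treats all the others as descriptive. Section 5 says: "There are no changes to the analyses planned as specified in the study protocol".

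**The concern.** Seven analyses change sidedness between the two documents (the primary, five binary secondaries and length of stay), and the section meant to list departures from the protocol says there are none. Tables are programmed from the SAP, so the study report would print p-values other than those the protocol promises, with no declared deviation to explain them.

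For a confirmatory test with its own threshold, the switch is harmless. A descriptive p-value has no decision rule attached; readers simply read it, usually against 0.05. A 1-sided 0.04 corresponds to a 2-sided 2 × 0.04 = 0.08, and would normally sit beside a 95% CI that includes zero. On mortality, in a trial giving CSL312 to COVID-19 patients for the first time (Protocol 1.4), a small p-value could flag a difference in only one direction.

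**Working it through.** **1. Does the switch touch the design?** The inputs are in Protocol 11.1: "a rate of 30% in the control group and a rate of 10% in the CSL312 group have been assumed", with 124 subjects (62 per arm) randomized "in order to achieve 80% power to detect a treatment difference using a 2 group chi-square test". For the pooled chi-square test without continuity correction:

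n per arm = [z_α √(2p̄(1 − p̄)) + z_β √(p₁(1 − p₁) + p₂(1 − p₂))]² / (p₁ − p₂)²

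with p̄ = 0.20, z_α = 1.960 and z_β = 0.842:

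n = [1.960 × √0.32 + 0.842 × √0.30]² / 0.20² = [1.109 + 0.461]² / 0.04 = 61.6, rounded up to 62 per arm, or 124 in total.

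The stated figure is reproduced. Power at 62 per arm is 80.3%. The critical value is 1.960 for both 2-sided 0.05 and 1-sided 0.025, so sample size, power and the threshold for claiming benefit are identical.

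**2. Where the documents differ on sidedness.**

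| Analysis | Protocol | SAP |
|---|---|---|
| Primary (Firth) | 2-sided (11.3) | 1-sided, 0.025 (10.1.2) |
| Five binary secondaries | 2-sided (11.4) | 1-sided (10.2.1) |
| Hospital length of stay (Cox) | 2-sided Wald (11.4) | 1-sided Wald (10.2.1) |
| SOFA (Wilcoxon) | not stated (11.4) | 1-sided by default (7) |

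The first three rows are replacements. The fourth is an addition. The version gap does not account for them: the SAP is based on Amendment 2, and the Amendment 3 log lists only contraception duration and a thermometer method.

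**3. Effect on the printed value.** Let P be the 2-sided p-value. A 1-sided p-value in the benefit direction is P/2 if the estimate favours CSL312 and 1 − P/2 if it favours placebo.

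| 2-sided P | SAP prints, favours CSL312 | SAP prints, favours placebo |
|---|---|---|
| 0.05 | 0.025 | 0.975 |
| 0.04 | 0.020 | 0.980 |
| 0.01 | 0.005 | 0.995 |

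**4. Illustration.** The counts are assumed, not taken from the documents, and the planned covariates are left out. Take 12/62 deaths on CSL312 and 4/62 on placebo. Adding 0.5 per cell:

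- log odds ratio = ln[(12.5 × 58.5) / (50.5 × 4.5)] = ln 3.218 = 1.169
- SE = √(1/12.5 + 1/50.5 + 1/4.5 + 1/58.5) = √0.339 = 0.582
- z = 1.169 / 0.582 = 2.01
- 2-sided p = 0.045; 1-sided p for benefit = 0.978

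The unadjusted risk difference is 8/62 = +12.9 percentage points, with Wald 95% CI +1.3 to +24.5. The mirror image (4 against 12) has the same 2-sided p of 0.045 and would print about 0.022 under the SAP.

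A second assumed pair, 15/62 against 6/62 in an unadjusted Firth model with a Wald test, gives 2-sided 0.041 and 1-sided 0.979, with a risk difference of +14.5 points (+1.6 to +27.5).

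**The case against.** The strongest reply is that nothing inferential turns on this. The SAP states its directional hypothesis, its 1-sided 0.025 level and the equivalence to 2-sided 0.05 openly, and says its decisions were made before the first unblinding for the IDMC. The secondaries are descriptive. A reader who applies 0.025 will find p-value and CI in agreement, apart from small differences of method. All of this stands, and it limits the point to reporting and consistency between documents. It does not make the no-change statement in SAP section 5 correct.

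A reader might infer that harm on mortality would be hidden. The documents do not support that. SAP 10.2.1 places counts, percentages, the risk difference and the 95% CI with the p-value; in the first illustration the interval excludes zero on the harmful side. A p-value above 0.975 is itself recognisable as an adverse result. SAP 11.2 adds fatal-event tables and a listing of deaths, and Protocol 8.1 provides unblinded IDMC review.

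A reader might also infer that every secondary p-value is halved. That is true only when the estimate favours CSL312.

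Nor are all tests switched from 2-sided: the protocol sets no sidedness for the Wilcoxon test. For the secondaries, the benefit direction is a reasonable inference from SAP 4.1.2 and the shared testing method, but no direction is written for each endpoint, for the hazard ratio or for SOFA.

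**Conclusion.** The inconsistency is real and undeclared. It covers the primary endpoint, five binary secondaries and hospital length of stay. It is not an inflation of type I error: 124 subjects, 80.3% power and the primary decision are the same either way.

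Its size is the change in the printed secondary p-values, P/2 or 1 − P/2 in place of P, so that an excess of deaths significant at 2-sided 0.05 prints as 0.975 or higher. The algebra does not depend on the illustrative counts. It does rest on reading the 1-sided secondary tests in the benefit direction. It is worth correcting because the SAP drives the outputs and the correction costs almost nothing.

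**What to change.** - **Secondaries.** In SAP 10.2.1, report 2-sided p-values for the five binary endpoints and hospital length of stay, as Protocol 11.4 says, and amend the 1-sided default in SAP 7 to match.
- **Primary.** In SAP 10.1.2, report a 2-sided p-value and claim benefit if it is below 0.05 with the effect favouring CSL312. This is identical to 1-sided 0.025. The tipping-point classification in 10.1.3.1 should follow the primary.
- **SOFA.** State the sidedness of the Wilcoxon test, preferably 2-sided for consistency.
- **If any 1-sided test is kept.** Correct SAP section 5 to declare the change, and label each such p-value with its direction and the 0.025 level. For length of stay, say which side of 1 is favourable: the event is discharge alive, so the favourable direction is a higher hazard on CSL312, opposite to the binary endpoints.

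The cost is SAP wording and table labels. Sample size, power, the primary decision and its error rate do not change.
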